7.5 Efficacy

7.5.1 Complete Remission Rate and Other Response Endpoints

The rate of subjects with complete remission (CR/CRi) will be summarized by a binomial response rate, and corresponding two-sided 95% exact CI using the Clopper and Pearson method. This will be based on best overall response prior to the initiation of any alternative therapy (including any subsequent ulocuplumab 800 mg for subjects in the LDAC alone arm). The rate will be based on all randomized subjects, except at DMC Interim #2, when the calculation will be based on response-evaluable subjects. The rate of OR (= CR/CRi/PR) will similarly be summarized.

- Best response and remission rates summary (best response categorization [CR, CRi, PR, TF]; rates of complete and overall remission)
- Best response listing (with overall response by visit, best response)
- Bone marrow blast assessments plot (% change from baseline)
- Bone marrow blast assessments listing (with bone marrow blast [%], % change from baseline, best reduction, presentation of Auer rods by visit)
- Extramedullary disease listing (disease presence and disease site)
- RBC transfusion listing (type of transfusion)

7.5.2 Overall Survival

OS will be estimated using Kaplan Meier (KM) methodology. Median OS will be estimated, along with two-sided 95% CIs using the Brookmeyer and Crowley method, considering a log-log transformation.

- KM plot of OS

7.5.3 Duration of Remission

For subjects who achieve CR or CRi, DoR will be estimated in the same way as OS.

- KM plot of DoR

7.5.4 Subsequent Therapy

- Summary of subsequent cancer therapy (number of subjects with any, radiotherapy, surgery, systemic therapy)
- Listing of subsequent cancer therapy

7.6 Safety

AEs will be coded according to the most current version of MedDRA and be graded using the NCI CTCAE version 4.03. Drug-related AEs are events with a relationship to study drug of 'Related' (as recorded on the CRF). If the relationship to study drug is missing, the AE will be considered drug-related.

Summaries of AEs will be based on on-treatment events, i.e. those occurring from the first dose date to up to 30 days (inclusive) after the last dose of study medication for subjects who are off-

treatment. Tables of AEs by CTC grade will be based on the event with worst CTC grade (independent of relationship to study medication). Subjects will only be counted (1) once at the preferred term (PT) level, (2) once at the system organ class (SOC) level, and (3) once in the 'Total subject' row, at their worst CTC grade, regardless of SOC or PT.

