4.6 Selection and Timing of Dose for Each Subject

Subjects were/will be assigned to a dose cohort in the order they enter the study.

Subjects in the escalation cohort received ulocuplumab at 600 or 800 mg administered as a single IV infusion on Day 1, 8 and 15 and LDAC at 20 mg BID (40 mg/day) subcutaneously administered on Day 1 - 10 in Cycle 1 (DLT evaluation period) and Cycle 2. Subjects then received ulocuplumab at 600 or 800 mg on Day 1 and 8 in combination with LDAC at 20 mg BID (40 mg/day) on Day 1 - 10 in Cycle 3 and subsequent cycles. A total of 3 subjects were treated at the dose level of 600 mg. A decision to consider the next higher dose level or the next lower dose level or to stop the enrollment upon judging the current dose to be safe was guided by the number of subjects with DLTs observed during the DLT evaluation period based on the mTPI design (see [Section 3.1.1](#)).

Subjects in the expansion cohort will receive ulocuplumab or LDAC alone. Subjects assigned to ulocuplumab arms will receive ulocuplumab 800 mg or ulocuplumab 1000 mg administered as a single IV infusion on Day 1, 8 and 15 and LDAC at 20 mg BID (40 mg/day) subcutaneously administered on Day 1 - 10 in Cycle 1 and Cycle 2. These subjects will then receive ulocuplumab at 800 mg or 1000 mg on Day 1 and 8 in combination with LDAC at 20 mg BID (40 mg/day) on Day 1 - 10 in Cycle 3 and subsequent cycles.

Subjects assigned to the LDAC alone arm will receive 20 mg BID (40 mg/day) on Day 1-10 in every cycle. If ulocuplumab is added to the LDAC alone arm after Cycle 4, the treatment schedule is LDAC 20 mg BID from Day 1 to 10 of each cycle and ulocuplumab 800 mg on day 1, 8 and 15 for the first 2 cycles then ulocuplumab 800 mg on Day 1 and 8 for subsequent cycles. Follow Treatment Procedural Outline ([Table 5.1-2](#)).

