2 STUDY DESCRIPTION

2.1 Schedule of Analyses

Phase 1 (escalation cohort) has previously been analyzed; the original SAP is attached as an appendix to this document. This SAP applies similar methodology to Phase 2 (expansion cohort), the following analyses of which are planned:

Table 1: Planned Analyses of Expansion Cohort

Meeting/Format	Timing	Purpose
DMC Interim #1	When the first 6 subjects in the ulocuplumab 1000mg arm have had opportunity for 28 days of follow-up	Review of all available safety data, especially pertaining to the ulocuplumab 1000mg dose; results will be available for review by BMS also
DMC Interim #2	When around 60 subjects (20 per treatment arm) have completed 2 months of treatment and follow-up	See DMC Charter for additional details; results will be available for review by BMS also
DMC Interim #3 (SAE only)	About 12 months after interim #2	See DMC Charter for additional details
Final analysis	After all patients have had opportunity for 6 months of follow-up	For final report (CSR)
DMC final meeting	When 100% of subjects have completed or discontinued from all study drugs	Review all safety data for the proposed treatment regimen and provide insight for potential future trials
Study completion analysis	At completion of study (subject follow-up complete)	Review mature OS data

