 - Note: for the LDAC alone arm, ulocuplumab 800 mg may be added on Days 1 and 8 (also on Day 15, in cycles 1-2) if a subject does not achieve CR or CRi confirmed by blast count reduction after 4 treatment cycles or if they relapse after achieving complete remission.
- Follow-up: a follow-up visit will be completed 30 (± 7) days from the last dose of study therapy. Subjects will continue to be followed every 3 months for ongoing drug-related AEs until they have resolved, returned to baseline or are deemed irreversible, or until loss to follow-up or withdrawal of study consent. Subjects will also be followed every 3 months for OS for up to two years, until death, loss to follow-up or withdrawal of study consent.

The study design schematic is presented in Figure 1. Further details of the study design may be found in [Section 3.1](#) of the Protocol.

Figure 1: Study Design Schematic

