6 STUDY PERIODS, TREATMENT REGIMENS AND POPULATIONS FOR ANALYSES

6.1 Study Periods

Within each phase, this study consists of three analysis periods: pre-treatment, on-treatment, and post-treatment.

- The pre-treatment period extends from the time of signing the informed consent form to prior to the first dose of study medication.
- The on-treatment period starts at the time of the first dose of study medication and ends 30 days following the last day of dosing (if a subject discontinues study medication).
- The post-treatment period begins after 30 days following the last day of dosing.

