6.2 Treatment Regimens

Unless otherwise specified, analyses will be performed by Phase 2 treatment arm:

- 1) ulocuplumab 800 mg in combination with LDAC 20 mg BID;
- 2) ulocuplumab 1000 mg in combination with LDAC 20 mg BID;
- 3) LDAC 20 mg BID alone.

Demographic and baseline characteristics, as well as (Phase 2) efficacy, will be summarized (in all randomized subjects) by treatment arm as randomized (per IWRS). Safety and exposure will be summarized (in all treated subjects) by treatment arm as treated. (In general, 'as treated' will be the same as 'as randomized'. However, if a subject received an incorrect drug for the entire period of treatment, the subject will be summarized according to the incorrect drug that the subject actually received.)

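### As written, the SAP counts safety events that occur after LDAC-alone subjects add ulocuplumab 800 mg in the LDAC-alone column, and lists no safety summary for the add-on period

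*SAP*

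**What the plan says.** **The add-on.** SAP 2.2 states that "for the LDAC alone arm, ulocuplumab 800 mg may be added on Days 1 and 8" (with Day 15 in the first two cycles) if there is no CR or CRi "after 4 treatment cycles or if they relapse after achieving complete remission". Protocol 4.6 keeps LDAC going during the add-on: "the treatment schedule is LDAC 20 mg BID from Day 1 to 10 of each cycle", with ulocuplumab alongside.

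**The window.** SAP 6.1 defines one on-treatment period, which "starts at the time of the first dose of study medication and ends 30 days following the last day of dosing". SAP 7.6 uses the same span for adverse events: "those occurring from the first dose date to up to 30 days (inclusive) after the last dose of study medication". SAP 7.6.6 takes the worst laboratory result up to the same end point.

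**The column.** SAP 6.2 states: "Safety and exposure will be summarized (in all treated subjects) by treatment arm as treated". The only reassignment rule applies "if a subject received an incorrect drug for the entire period of treatment". SAP 7.1 makes treatment group the default for every analysis unless something else is specified, and nothing in 7.6 to 7.6.8 specifies otherwise for add-on subjects.

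**Where the add-on is recognised.** SAP 4.1.1 and 7.5.1 cut best response at the add-on. SAP 7.3.1 plans a separate status summary for the added ulocuplumab period. SAP 7.4.1 summarizes ulocuplumab duration and number of infusions separately from LDAC duration.

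**The concern.** The third safety column is labelled as LDAC 20 mg BID alone. For a subject who adds ulocuplumab, it would hold both LDAC-alone and combination experience, with nothing in the table to separate them. The affected summaries are AEs, drug-related AEs, SAEs, AEs leading to discontinuation, worst-grade laboratory results and exposure-adjusted AEs. SAP 7.6 defines drug-related by relation to study drug, so a reaction the investigator attributes to ulocuplumab would count as drug-related under LDAC alone.

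With no inferential testing planned, the descriptive tables are the safety result, so each column should contain what its label says. This is also the only arm that starts without ulocuplumab, so readers will look to it for background toxicity. The safety of ulocuplumab with LDAC is a secondary objective (SAP 3.2), yet no safety summary would show these subjects as ulocuplumab-exposed.

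**Working it through.** The plan gives no safety figure for this point. Its only Phase 2 design figures are the exact 95% intervals for a response rate with 40 subjects (Protocol 8.1, SAP 5). They reproduce by Clopper-Pearson: 24/40 gives 0.433 to 0.751 (stated 0.43 to 0.75), and 18/40 gives 0.293 to 0.615 (stated 0.29 to 0.62). The point does not depend on them.

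**Following one subject through the rules**

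1. Randomized to LDAC alone, no CR/CRi after 4 cycles, adds ulocuplumab 800 mg as permitted.
2. Is the window still open? LDAC is the study medication for this arm in the SAP 6.3 definition of treated subjects, and it continues. The last dose has not occurred, whether or not the added ulocuplumab also counts as study medication.
3. Does the column change? The subject did not receive an incorrect drug, and did not receive ulocuplumab for the whole treatment period. The SAP 6.2 exception does not apply.
4. Does any output in 7.6 to 7.6.8 override the default grouping? None does. Protocol 8.4.3 says only that adverse events are tabulated by treatment.

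The subject's later events therefore fall in the LDAC-alone column.

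**Can there be add-on time by the final analysis?** Cycle length is 28 days (SAP 2.2), and the final analysis follows an opportunity for 6 months of follow-up (SAP 2.1).

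- Four cycles: 4 × 28 = 112 days.
- Six months: 6 × 365.25/12 = 182.6, about 183 days.
- Difference: 183 − 112 = 71 days.
- An on-schedule subject who starts the add-on on Day 113 could have infusions on Days 113, 120, 127, 141, 148, 155, 169 and 176, which is 8.

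This is the most that the last subject to enrol could have on schedule; dose delays reduce it, and earlier-enrolled subjects can have more.

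**Effect per subject.** With 40 planned LDAC-alone subjects, one whose first event falls in the add-on adds 1/40 = 2.5 points to crude incidence. One whose worst-grade event falls there moves 2.5 points from a lower to a higher grade row. An exposure-adjusted rate becomes (E1 + E2)/(T1 + T2), where E is events and T is time at risk before (1) and during (2) the add-on. It can move either way.

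**Illustration with assumed rates only.** Let m of 40 subjects add ulocuplumab, p0 be incidence before the add-on (the same in switchers and non-switchers), and pn be the chance of an event during the add-on, independent of what came before. The uncut column rises by (m/40) × (1 − p0) × pn. With p0 = 30%:

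| m | pn = 30% | pn = 50% |
|---|---|---|
| 4 | 0.10 × 0.7 × 0.3 = 2.1 points | 0.10 × 0.7 × 0.5 = 3.5 points |
| 10 | 0.25 × 0.7 × 0.3 = 5.25 points | 0.25 × 0.7 × 0.5 = 8.75 points |
| 20 | 0.50 × 0.7 × 0.3 = 10.5 points | 0.50 × 0.7 × 0.5 = 17.5 points |

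A column cut at the add-on would show 30% throughout. None of these rates comes from the documents.

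**The case against.** **No sentence assigns add-on events to the LDAC-alone column.** True. The separate disposition summary even hints that the sponsor sees two treatment periods. But SAP 6.1 and 6.2 set the window and the column by general rules, and add-on subjects meet both. The result follows from stated rules.

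**Details are deferred.** SAP 7.1, 8 and 9 point to the DPP, the DMC Charter and the sponsor's safety conventions. These were not available and could contain a split. This stands as a limit: a reader should not infer that no rule exists anywhere. If one does, the SAP needs only a citation.

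**The consequence is limited.** This also stands. The cohort is described as non-comparative, SAP 2.4 rules out inferential testing between groups, and the documents do not name LDAC alone as a formal safety comparator. A reader might infer a biased safety comparison or a masked harm, and the plan supports neither. The ulocuplumab columns are untouched, listings keep every event, and SAP 7.4.1 would make add-on exposure visible. A listing, though, gives no denominator or rate.

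**Few subjects may reach the add-on.** Eligibility asks for a life expectancy of at least 12 weeks (84 days), less than the 112 days to non-response, and cycle delays are allowed. The number is unknown.

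**Interim #2.** Its trigger is "When around 60 subjects (20 per treatment arm) have completed 2 months of treatment and follow-up", and SAP 7.1 produces these tables then. A reader might infer that early relapse puts add-on exposure into that interim before 4 cycles, because SAP 2.2 attaches no wait to relapse. Protocol 4.6, however, refers to ulocuplumab being added after Cycle 4. The passages on add-on timing need reconciling, and the inference should not be drawn. Two months is a minimum, so earlier-enrolled non-responders could be past 112 days, but no accrual rate is given to say whether any would be.

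**Deaths.** A reader might also fault the all-deaths row in SAP 7.6.1 for including deaths after the add-on. An unwindowed count by arm is legitimate and is not an error.

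**Conclusion.** The point holds on the SAP text. Under 6.1, 6.2 and 7.6, events on LDAC plus added ulocuplumab are summarized as LDAC alone, and no safety summary covers the add-on period. The column would not match its label.

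The size cannot be stated beyond 2.5 points of LDAC-alone incidence per affected subject, assuming 40 treated. Nor would every such event be due to ulocuplumab: LDAC, the disease and extra time at risk contribute. No primary endpoint or test is affected. This is a cheap improvement to make before the tables are produced, and it is conditional on the DPP and safety conventions not already containing the rule.

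**What to change.** In SAP 6.1, 6.2 and 7.6:

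- Add a treatment-period flag at the first added ulocuplumab dose.
- Summarize LDAC-alone AEs, drug-related AEs, SAEs, AEs leading to discontinuation, laboratory results and the already planned exposure-adjusted AEs before that dose.
- Summarize later events, to 30 days after last dose, in a separate column, *LDAC alone, then + ulocuplumab 800 mg*, with its own denominator and exposure. Do this in every analysis that has add-on exposure.
- Keep the uncut table as a supportive output, labelled as the LDAC arm including added ulocuplumab.
- Leave the all-deaths row by arm, and identify in it the deaths after the add-on.
- If the DPP or safety conventions already hold such a rule, cite it in SAP 7.6 instead.

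The cost is one derived flag, one extra column in the affected tables and one supportive set, with no new data collection. The drawback is that the cut shortens LDAC-alone follow-up selectively in non-responders and relapsers, and moves events soon after the last LDAC-only dose into the new column. The retained uncut table is there for that reason.

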The expansion cohort will treat approximately an additional 120 subjects at a dose of 800 mg or 1000 mg ulocuplumab in combination with LDAC or LDAC alone. Sample size is discussed in [Section 8.1](#). All assessments from the escalation cohort will be performed and additional assessments (eg, biomarkers) are noted in [Table 5.1-1](#), [Table 5.1-2](#), [Table 5.1-3](#), [Table 5.5.1-1](#), [Table 5.5.1-2](#), and [Table 5.7.2-1](#).

Follow-up

- Begins when the decision to discontinue a subject from study therapy is made (no further treatment with study therapy).
- Subjects will have one follow-up visit for safety. Follow-up visit 1(X01) will be completed 30 days (\pm 7 days) from the last dose of study therapy. After X01, subjects will be followed

every 3 months for ongoing drug-related AEs until resolved, return to baseline or deemed irreversible, or until lost to follow-up or withdrawal of study consent. Subjects will also be followed every 3 months for survival for up to two years, until death, lost to follow-up or withdrawal of study consent.

- PK, immunogenicity and biomarker samples will be collected at the 30 day follow-up visit.

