Adverse Events	X		All abnormal findings and any new or worsening signs and/or symptoms are to be recorded as AEs after study drug administration. All AEs must be collected from the initiation of study drug until 30 days after the end of treatment.

Table 5.1-3: Follow-up Assessments (CA212016)

Procedure	X, Follow-up Visit - 30 days ^{a,b}	S, Survival Follow-up Visits ^c	Notes
PK Assessments			Study drug-related AEs that are reported/identified during the follow up period should be followed to resolution, stabilization, or initiation of new therapy or until deemed irreversible.
Serum sample for PK	X		Applies to Ulocuplumab/LDAC combination arms only See Table 5.5.1-1
Immunogenicity Assessments			
Serum sample for immunogenicity	X		Applies to Ulocuplumab/LDAC combination arms only See Table 5.5.1-1
Efficacy Assessments			
Bone marrow aspirate/biopsy	X		The results of the local lab bone marrow aspirate (or biopsy) done as part of routine care will be sent to BMS. Bone marrow aspirate is sufficient for the leukemia response evaluation. The marrow must be of adequate recovery and cellularity for evaluation. If the bone marrow has not yet recovered, repeat the bone marrow until a leukemia response can be determined. The next cycle of treatment is delayed until the marrow is of adequate recovery and cellularity for a response assessment to be completed.
Diagnostic testing for extramedullary disease	X		Testing for extramedullary disease as part of subject's routine care, if clinically indicated.
RBC transfusion requirements	X		The threshold for transfusion will be determined at the investigator's discretion.
			

Table 5.1-3: Follow-up Assessments (CA212016)

Procedure	X, Follow-up Visit - 30 days ^{a,b}	S, Survival Follow-up Visits ^c	Notes
[REDACTED]			
Subject Status			
Survival Status	X	X	Every 3 months after X01; may be accomplished by visit or phone contact, to update survival information and assess subsequent anti-cancer therapy

a Subjects who discontinue ulocuplumab combination or LDAC alone treatment for any reason will be followed for 30 day after the end of treatment visit.

b A window of ± 7 days is permitted.

c A window of ± 30 days is permitted.

[REDACTED]

The end of treatment visit should be performed on the day a decision is made to discontinue study treatment. In the event of multiple procedures are required at a single time point, the following is a list of procedures from highest priority to low:

1. PK and RO Sampling

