^c If infusion has not completed at 1 hour, then draw PK sample immediately after the infusion ends and record time accurately.

^d The Day 1 and Day 8 pre-dose and end of infusion samples to be collected at Cycle 3 and every cycle thereafter until Cycle 5.

^e Follow-up visit should occur no less than 30 days after the end of treatment visit

Table 5.5.1-2: Ulocuplumab PK and RO Sampling Schedule (Expansion Cohort, Sparse Sampling Subset)

Study Day	Time (Relative to Dosing) Hour	Time (Relative to Dosing) Hour: Min	PK Blood Sample	RO Sample	ADA Sample
Cycle 1, Day 1	0 (pre-dose)	00:00	X	X	X
	1.0 (end of infusion) ^a	01:00	X	X	
Cycle 1, Day 8	0 (pre-dose)	00:00	X	X	
	1.0 (end of infusion) ^a	01:00	X	X	
Cycle 1, Day 15	0 (pre-dose)	00:00	X	X	X
	1.0 (end of infusion) ^a	01:00	X	X	
Cycle 2, Day 1	0 (pre-dose)	00:00	X	X	X
	1.0 (end of infusion) ^a	01:00	X	X	
Cycle 2, Day 8	0 (pre-dose)	00:00	X	X	
	1.0 (end of infusion) ^a	01:00	X	X	
Cycle 2, Day 15	0 (pre-dose)	00:00	X	X	
	1.0 (end of infusion) ^a	01:00	X	X	
Cycle 3-5, Day 1 ^b	0 (pre-dose)	00:00	X	X	X
	1.0 (end of infusion) ^a	01:00	X	X	
Cycle 3-5, Day 8 ^b	0 (pre-dose)	00:00	X	X	
	1.0 (end of infusion) ^a	01:00	X	X	
Every 4 Cycles after Cycle 5, Day 1	0 (pre-dose)	00:00	X		X
End of Treatment			X		X
Follow-up ^c			X		X

^a If infusion has not completed at 1 hour, then draw PK sample immediately after the infusion ends and record time accurately.

^b The Day 1 and Day 8 pre-dose and end of infusion samples to be collected at Cycle 3 and every cycle thereafter until Cycle 5.

^c Follow-up visit should occur no less than 30 days after the end of treatment visit.

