4.2 Secondary Safety Endpoints

Safety and tolerability will be assessed through AEs, AEs leading to discontinuation, SAEs, deaths and laboratory abnormalities in combination therapy during the treatment period plus 30 days of follow-up. AEs will be graded according to NCI CTCAE v4.03.

Triplicate measurements of each serial ECG will be used to obtain an average value for each time point. Baseline will be defined as the time point prior to dosing on the first day of Cycle 1. All available non-missing values of ECG parameters should be used in the analyses. However:

- if QTcF is missing and RR in seconds is available, then QTcF will be calculated as $QTcF = QT / RR(1/3)$;
- if both QTcF and RR in seconds are missing, then QTcF will be calculated as $QTcF = QT / (60 / HR)(1/3)$.

The primary ECG endpoint is $\Delta QTcF$, the change from baseline in QTcF, the QT interval normalized using Fridericia's heart rate correction. Other endpoints include QTcF, QT, QRS, PR, HR (heart rate), and QTcB as well as ΔQT , ΔQRS , ΔPR , ΔHR (heart rate), $\Delta QTcB$, the associated changes from baseline. (Note: QTcB is the QT interval normalized using Bazett's heart rate correction.)

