7.6.6 Clinical Laboratory Evaluations

Laboratory results will be categorized according to NCI CTCAE grade. Analyses will be based on the international system (SI) of units, but will be repeated using US units.

Baseline is defined as the last non-missing measurement prior to the first dosing date and time. Summaries of laboratory results will compare baseline with the worst post-baseline result (up to 30 days [inclusive] after the last dose of study medication for subjects who are off-treatment).

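### SAP safety tables close 30 days after last dose while the protocol collects AEs to 30 days after end of treatment, and the protocol's own follow-up anchors disagree

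*SAP*

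**What the plan says.** **What is tabulated (SAP).** Once a subject has stopped treatment, the AE summaries in 7.6 are restricted to events "those occurring from the first dose date to up to 30 days (inclusive) after the last dose of study medication". Laboratory summaries in 7.6.6 compare baseline with the worst later result "up to 30 days [inclusive] after the last dose of study medication for subjects who are off-treatment". Section 6.1 ends the on-treatment period at the same point. The safety endpoint in SAP 4.2, however, covers AEs and "laboratory abnormalities in combination therapy during the treatment period plus 30 days of follow-up".

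**What is collected (Protocol).** Tables 5.1-2 and 5.1-3 state: "All AEs must be collected from the initiation of study drug until 30 days after the end of treatment". Section 3.1 says the same with reference to the end-of-treatment visit, and starts follow-up at the decision to discontinue. Section 5.1 fixes the date: "The end of treatment visit should be performed on the day a decision is made to discontinue study treatment". Section 8.4.3 has all recorded AEs listed and tabulated, with no cut-off.

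**Other anchors in the protocol.** Section 3.1 places visit X01 at 30 ± 7 days "from the last dose of study therapy". The footnotes to Tables 5.5.1-1 and 5.5.1-2 say: "Follow-up visit should occur no less than 30 days after the end of treatment visit". Section 6.1.1 collects all SAEs to 30 days after discontinuation of dosing, and later ones only if believed related.

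**Length of a hold.** Section 4.6.1.2 allows delays of up to 28 or 42 days before Cycle 2 (by type of toxicity) and up to 56 days from Cycle 3 on. After Cycle 1, one drug may continue while the other is held (4.6.1).

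**The concern.** Last dose and end of treatment are different dates whenever a hold precedes the decision to stop. The SAP counts from the first and the protocol's AE collection from the second, so some events are collected and then left out of the summaries.

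The omission depends on what happens next. The SAP limit applies to subjects who are off treatment and runs from their last dose. Take an infection with onset on day 45 of a hold. If dosing resumes, the last dose moves later and the event is tabulated. If treatment is stopped, the same event is not. The tables thus lose late events selectively from subjects who did not recover enough to continue.

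At stake are new-onset events late in a hold or soon after the stop decision, including an AE that itself led to discontinuation. A fatal AE in that interval would appear in the all-deaths summary but not in the Grade 5 column of the AE or SAE tables, so outputs could disagree.

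**Working it through.** The plan gives no figure to reproduce; this is day arithmetic on the stated windows.

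**Definitions**, in days after the last dose of any study drug:
- H = day of the end-of-treatment visit
- SAP tables close at day 30 (SAP 6.1, 7.6, 7.6.6)
- AE collection closes at day H + 30 (Protocol 3.1, Tables 5.1-2 and 5.1-3)
- Untabulated days = (H + 30) − 30 = H
- Of these, max(0, H − 30) lie in the hold and min(30, H) after end of treatment

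| Case | H | Collection closes | Untabulated | In hold | After end of treatment |
|---|---|---|---|---|---|
| No hold, last dose Day 15, end of treatment Day 28 (assumed) | 13 | 43 | 13 (30%) | 0 | 13 |
| No hold, last dose Day 10, end of treatment Day 28 (assumed) | 18 | 48 | 18 (38%) | 0 | 18 |
| Both drugs held 42 days | 42 | 72 | 42 (58%) | 12 | 30 |
| Both drugs held 56 days | 56 | 86 | 56 (65%) | 26 | 30 |
| Last dose Day 10, 56-day delay counted from Day 28 (assumed) | 74 | 104 | 74 (71%) | 44 | 30 |

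The 42- and 56-day rows count the hold from the last dose. The protocol does not say exactly where a delay starts, so the last row shows the effect of counting from the end of the cycle (18 + 56 = 74). The first two rows show that a smaller mismatch exists with no hold.

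**Visit anchors.** X01 is due on days 30 − 7 = 23 to 30 + 7 = 37 after last dose. The PK-table footnotes put the follow-up visit at day H + 30 or later. Both can be met only if H + 30 ≤ 37, that is H ≤ 7. For H above 37, the whole X01 window has passed before the end-of-treatment visit. With H = 56, X01 is due by day 37, end of treatment is day 56, and the PK-table visit is day 86 or later.

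**The case against.** **The last-dose window is conventional, and the protocol supports it in part.** All-cause SAE collection is tied to discontinuation of dosing and X01 to last dose. The SAP took one of several anchors in the protocol. This stands: collection to day 86 holds only where the end-of-treatment rule governs, and the root problem is partly the protocol's own inconsistency.

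**A reader might infer that toxicity during a long hold is lost.** The documents do not support that. The event that triggered the hold and the first 30 days after last dose are tabulated; in the 56-day case, 26 hold days fall outside. AE and SAE listings (SAP 7.6.2, 7.6.4) state no such cut-off, and 7.6.1 summarises all deaths. The full gap also needs both drugs held.

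**A reader might infer that prolonged marrow suppression would be hidden.** This is weak. Tables use the worst grade or worst result, which would usually occur within the first 30 days. The DLT and discontinuation criteria are applied to individual subjects (Protocol 4.6.1, 5.3.1), not read from these summaries.

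**A reader might argue from residual exposure**, since the protocol's 5 half-lives are 48 days. That gives 48/5 = 9.6 days per half-life and about 0.5^(30/9.6) ≈ 11% remaining at day 30. The argument favours a window tied to last dose, not to the decision date, and has no bearing on LDAC-alone subjects who never add ulocuplumab.

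**Replacing the main window has costs.** Other systemic anti-cancer therapy is allowed in follow-up (Protocol 3.4.2), so a longer window could admit its toxicity. Its length would also vary with how long each investigator waits before stopping. This stands, and is why the remedy is an added table.

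**Further conventions lie elsewhere.** SAP 8 refers to the data presentation plan and a safety-data SOP, which are not available here. They might add such a summary, but the SAP text does not say so.

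**Conclusion.** The mismatch is real, but its reach is limited. For subjects who stop treatment, new-onset AEs and laboratory results more than 30 days after the last dose of any study drug are left out of the summary tables, though Protocol 8.4.3 would tabulate all recorded AEs and the endpoint covers the treatment period plus 30 days of follow-up. The untabulated interval equals the gap between last dose and end of treatment: up to 56 of 86 days when both drugs are held for 56 days, 42 of 72 at 42 days, and 13 to 18 days with no hold on the assumptions shown.

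These figures assume that the end-of-treatment + 30-day rule governs AE collection. They measure calendar time, not events: the documents give no frequency of long holds, so the number of events affected cannot be computed. Separately, the follow-up timings in the protocol cannot all be met once end of treatment is more than 7 days after last dose. Safety is a secondary objective of an exploratory, non-comparative Phase 2 cohort, so this is an inexpensive improvement and not a defect in the primary analysis.

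**What to change.** 1. **Keep last dose + 30 days as the main table.** It is conventional, and the Phase 1 SAP in the appendix uses the same AE window.
2. **Add one supplementary set to SAP 7.6 and 7.6.6:** AEs, SAEs and worst laboratory results to the later of last dose + 30 days and end-of-treatment visit + 30 days, cut at the start of subsequent anti-cancer therapy. State whether ulocuplumab added in the LDAC-alone arm triggers that cut, since the primary endpoint treats it as alternative therapy.
3. **Reconcile the X01, AE and SAE anchors** in Protocol 3.1, 5.1, 5.5.1 and 6.1.1 with each other and with SAP 2.2, 4.2 and 6.1, and reconcile the tabulation statement in Protocol 8.4.3 with SAP 7.6. Until this is done, footnote the supplementary SAE table to say that unrelated SAEs may not have been collected throughout the longer window.

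**Cost:** one extra set of tables and a protocol clarification. The AE part uses data that the protocol already requires. The supplementary tables will include some late disease-related events, and their window will vary with the timing of the stop decision; showing both sets side by side makes that visible.
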